6.5.3.2 Data Submission

Once required testing has been performed, complete and submit the appropriate forms to St. Jude Medical. Refer to Table 5: Study Procedures and Data Collection. It is recommended that the following device printouts and measurements be maintained at the site.

- FastPath Summary
- Test Results with Freezes, Include Battery & Leads
- Wrap-up Overview with full parameters
- Upload device session record

6.6 VT/VF Data Collection Effort

6.6.1 Induction Testing

6.6.1.1 Sub Study Induction Testing

Subjects that will participate in the induction testing sub study signed the consent for this sub study prior to or during the baseline visit of the MRI Ready IDE study. For sub study subjects, suggest that testing occurs within 30 days after MRI scan visit (-7/+14 days).

Clinical Investigational Plan

Conduct induction testing. The method of induction is physician preference

Evaluate subject for ADE, SADE, and UADE (for US sites) or USADE (for OUS sites) events and submit on AE CRF (as applicable). Report deviations, death, withdrawal, and out of service as applicable

Upload the device session records from the induction therapy testing.

6.6.1.1.1 Data Submission

Once required testing has been performed, complete and submit the appropriate forms to St. Jude Medical. Refer to Table 5: Study Procedures and Data Collection

6.6.1.2 Induction testing for clinical reasons

If a subject experiences reduced R waves or has other clinical needs for induction testing during a follow up visit after the MRI, then the physician may decide if the subject would benefit from induction testing.

A single induction test may be completed. The method of induction is physician preference.

Evaluate subject for ADE, SADE, and UADE (for US sites) or USADE (for OUS sites) events and submit on AE CRF (as applicable). Report deviations, death, withdrawal, and out of service as applicable

Upload the device session records from the induction therapy testing.

6.6.1.2.1 Data Submission

Once required testing has been performed, complete and submit the appropriate forms to St. Jude Medical. Refer to Table 5: Study Procedures and Data Collection.

6.6.2 Non-sub study subjects: Review of spontaneous VT/VF episodes

All enrolled subjects that are not enrolled in the sub study will also be followed via Merlin.net to capture events as they occur any time after the 1 month post MRI scan visit or phone call every 3 months post baseline for subjects that are not on Merlin.net to collect potential spontaneous VT/VF episodes that occur after the MRI visit.

Clinical Investigational Plan

If the subject is on Merlin.net and experienced a VT/VF episode, then the episodes will be collected by SJM from session records at the 1 month post MRI visit and from Merlin.net as they occur any time after the 1 month post MRI scan.

If the subject is not on Merlin.net, then the site will contact the subject by phone every 3 months post baseline \pm 30 days to find out if the subject has experienced a VT/VF tachyarrhythmia. If the subject has experienced a VT/VF tachyarrhythmia, then the subject will be asked to visit the clinic so that the session records may be obtained.

The review of Merlin.net records and/or follow up phone calls to subjects will end when SJM has collected a minimum of 25 subjects with at least one ventricular arrhythmia episode (spontaneous or induced) adjudicated by the Ventricular Arrhythmia Events Committee or until notification from SJM.

6.6.2.1 Data Submission

Once required testing has been performed, complete and submit the appropriate forms to St. Jude Medical. Refer to Table 5.

If an ADE, SADE, and UADE (for US sites) or USADE (for OUS sites) events has occurred, submit an AE CRF (as applicable). Report withdrawal and out of service as applicable. Upload device session records through the EDC study site portal (as applicable).

6.7 Complete System Explants

If the subject has the entire Ellipse VR ICD system removed at any time during the study, and the subject will not receive a replacement Ellipse ICD system, follow the subject for 30 days, and withdraw the subject from the study. Complete a Product Out of Service CRF and submit through EDC. A System Revision CRF is not required to be submitted.

6.8 System Revisions

In cases where only the device pocket is revised (leads are not repositioned, leads have not been disconnected from the ICD), a System Revision CRF is not required to be submitted. A System Revision CRF should be completed for all other types of revisions such as pulse generator replacement, lead replacement and lead repositioning. The subject's follow up schedule is not affected in any way.

Clinical Investigational Plan

6.8.1 Revisions Before the MRI Scan

A system revision is defined as a replacement of or repositioning of one or more components of the study ICD system (Durata or Optisure lead, Ellipse VR ICD) that occurs after the subject has been consented into the study. Because all components of the study ICD system are market-released, all procedures related to the revision should be performed according to standard of care. The revision may be performed by either a study investigator or other clinician qualified to perform such procedures.

Any explanted devices or leads (including damaged leads, lead segments and lead fragments) should be returned to St. Jude Medical promptly for analysis. Document any change to the status of the lead and device (e.g. capped, removed) on the Product Out of Service CRF.

Refer to Table 5: Study Procedures and Data Collection to determine which case report forms need to be completed and submitted.

Refer to Table 8: System Revision Scenarios Prior to MRI Scan below to determine what actions need to be performed.

Clinical Investigational Plan

Table 8: System Revision Scenarios Prior to MRI Scan

System Revisions that occur prior to MRI Scan	Action	Data Submission

Revisions where the Ellipse ICD system is still implanted:
 
 • Durata or Optisure lead or the Ellipse ICD is repositioned or replaced, AND • The Ellipse AND Durata or Optisure lead are still implanted, AND • No other non-MRI compatible material has been implanted 	
Obtain (if possible):
 
 ○ In-clinic bipolar capture threshold at a pulse width of 0.5 ms for the applicable lead(s). Either the manual decrement or automatic (in-clinic, programmer based) method may be used to obtain the capture threshold. ○ In-clinic bipolar sensing amplitude for the applicable lead(s). Either the incremental or the automatic (in-clinic, programmer based) method may be used to obtain the sensing threshold. ○ In clinic Bipolar lead pacing impedance for the applicable lead ○ In clinic HVLI impedance for the applicable lead ○ Retain the subject in the study. If the MRI scan visit has not occurred yet, then wait at least 60 days from the successful revision before completing the MRI scan visit. If the MRI scan visit has occurred, then follow the subject through the 1 Month Post Scan visit. 	
Complete and submit the appropriate forms to St. Jude Medical. Refer to Table 5: Study Procedures and Data Collection. It is recommended that the following device printouts and measurements be maintained at the site.
 
 ○ FastPath Summary ○ Test Results with Freezes, Include Battery & Leads ○ Wrap-up Overview with full parameters

Revisions where the Ellipse ICD system is not retained and the MRI Settings have not been
	
The patient is a screen failure.
	
Document consenting information (name of the study, date of consent and inclusion/exclusion) in the subject’s medical and/or study records.
 
Submit the Baseline CRF and Screening Failure

Clinical Investigational Plan

programmed
 
 • Durata or Optisure or the Ellipse ICD was explanted but was not replaced with another Durata or Optisure or the Ellipse ICD, and/or • A non-MRI compatible material(s) or device(s) was implanted 		
CRF. Submit Deviation, Product Out of Service, or Death CRFs if applicable.
 
It is recommended that the following device printouts and measurements be maintained at the site.
 
 o FastPath Summary o Test Results with Freezes, Include Battery & Leads o Wrap-up Overview with full parameters

Revisions where the Ellipse ICD system is not retained and the MRI Settings were programmed
 
 • Durata or Optisure or the Ellipse ICD was explanted but was not replaced with another Durata or Optisure or the Ellipse ICD, and/or • A non-MRI compatible material(s) or device(s) was implanted 	
The patient will be withdrawn from the study.
	
Document consenting information (name of the study, date of consent and inclusion/exclusion) in the subject’s medical and/or study records.
 
Submit the Baseline CRF, Pre-MRI CRF, and Withdrawal CRF. Submit Deviation, Product Out of Service, or Death CRFs if applicable.
 
It is recommended that the following device printouts and measurements be maintained at the site.
 
 o FastPath Summary o Test Results with Freezes, Include Battery & Leads o Wrap-up Overview with full parameters

Clinical Investigational Plan

6.8.2 Revisions After the MRI scan

All subjects are enrolled in the study once the subject signs the main study consent, meets all of the inclusion criteria and none of the exclusion criteria, and the MRI Settings are enabled. If a system revision occurs after the MRI scan, then the subject will remain in the study until the subject completes the 1 Month Post Scan visit.

Any explanted devices or leads (including damaged leads, lead segments and lead fragments) should be returned to St. Jude Medical promptly for analysis. Document any change to the status of the lead and device (e.g. capped, removed) on the Product Out of Service CRF.

Refer to Table 9: System Revision Scenarios After MRI Scan below to determine what actions need to be performed.

Note: If a system revision occurs after the MRI scan visit, sites are encouraged to complete induction testing on the new Ellipse VR ICD during the procedure to assist in the collection of VT/VF episodes. Sites will be notified when a minimum of 25 subjects with at least one ventricular arrhythmia episode (spontaneous or induced) adjudicated by the Ventricular Arrhythmia Events Committee have been collected..

Table 9: System Revision Scenarios After MRI Scan

Table with 3 columns: System Revisions that occur after the MRI Scan, Action, and Data Submission. It details procedures for system revisions where the Ellipse ICD system is still implanted or replaced, including actions like obtaining capture and sensing thresholds and data submission requirements.

Clinical Investigational Plan

 • No other non-MRI compatible material has been implanted 	
undergoes a revision of the Ellipse VR device after the MRI visit and the Durata/Optisure lead remains in its original location, then induction testing could be performed during the system revision on the new Ellipse VR ICD.
 
 • Continue to follow the patient until the subject completes the 1 Month Post scan visit. 	

Revisions where the Durata/Optisure lead is not retained
 
 • Durata or Optisure lead is replaced with another lead, AND • The Ellipse VR ICD is still implanted, AND • A non-MRI compatible material(s) or device(s) has been implanted 	
Follow the subject for 30 days post system revision and then withdraw the subject from the study.
	
Document consenting information (name of the study, date of consent and inclusion/exclusion) in the subject’s medical and/or study records.
 
Submit the Baseline CRF, and Pre-MRI CRF, MRI CRF, System Revision CRF and Withdrawal CRF. Submit Deviation, Product Out of Service, Adverse Event or Death CRFs if applicable.
 
It is recommended that the following device printouts and measurements be maintained at the site.
 
 o FastPath Summary o Test Results with Freezes, Include Battery & Leads o Wrap-up Overview with full parameters

Revisions where the Ellipse ICD is not retained
 
 • Ellipse VR ICD is replaced with another Ellipse VR ICD, AND • Durata or Optisure lead is still implanted, AND • A non-MRI compatible material(s) or device(s) has been implanted 	
Continue to follow the subject until the subject completes the 1 Month Post scan visit.
	
Once required testing has been performed, complete and submit the appropriate forms to St. Jude Medical. Refer Table 5: Study Procedures and Data Collection

Clinical Investigational Plan

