12.1.1 Primary Safety endpoint

The primary safety endpoint #1 is: Freedom from MRI scan-related complications related to the Ellipse VR ICD involving Durata or Optisure (RV) lead from MRI scan to 1 month post MRI scan testing.

Hypothesis

The hypothesis is formally expressed as:

$$H_0: p_S \leq 90\%$$

$$H_a: p_S > 90\%$$

where p_S is the freedom from MRI scan-related complications(s) for the Durata or Optisure RV lead from MRI scan to 1 month after the MRI scan.

Analysis

The primary analysis will be conducted on subjects who meet all of the following criteria:

- Implanted with St. Jude Medical Durata or Optisure (RV) Lead
- Sign informed consent
- Meet the MRI Conditions of Use
- Undergo a Study MRI scan
- Have 1 month post-MRI scan visit or have MRI-scan related complication(s) for the Ellipse VR ICD involving Durata or Optisure RV lead before the 1 month post MRI visit

Clinical Investigational Plan

The hypothesis will be tested at the 2.5% significance level. The null hypothesis will be rejected if the 97.5% lower confidence bound for p_S is greater than 90%. The 97.5% lower confidence bound will be calculated by the exact (Clopper-Pearson) method for binomial probabilities.

12.1.2 Primary Efficacy Endpoint #1 (Change in Capture Threshold for Durata and Optisure (RV) Leads)

The primary efficacy endpoint #1 is the proportion of Durata or Optisure (RV) leads implanted with the Ellipse VR ICD with capture threshold increase of $\leq 0.5V$ at 0.5ms from pre-MRI scan to 1 month post-MRI scan testing.

Hypothesis

Success is defined as ventricular capture threshold increase of $\leq 0.5V$ at 0.5ms for the Durata or Optisure (RV) lead from pre-MRI scan testing to 1 month post-MRI scan.

The hypothesis is formally expressed as:

$$H_0: p_{E1} \leq 90\%$$

$$H_a: p_{E1} > 90\%$$

where p_{E1} is the probability of success.

Analysis

The primary analysis will be conducted on subjects who meet all of the following criteria:

- Implanted with the Durata or Optisure RV lead and Ellipse VR ICD
- Sign Informed consent
- Meet the MRI Conditions of Use
- Undergo a Study MRI scan
- Have MRI visit data for right ventricular capture threshold
- Have 1 month post-MRI scan visit data for RV capture threshold
- Have not undergone any VR ICD lead repositioning or replacement since the MRI scan up to 1 month post-MRI scan

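### The 6.8.2 text and one Table 9 row set different study-exit rules after a post-scan lead replacement, and withdrawal can precede a late 1-month visit

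*Combined protocol and SAP*

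**What the plan says.** - **Section 6.8.2, text.** If a revision occurs after the scan, "the subject will remain in the study until the subject completes the 1 Month Post Scan visit". Section 6.8 adds that a revision leaves the follow-up schedule unchanged.
- **Table 9, lead not retained.** The first condition is "Durata or Optisure lead is replaced with another lead, AND"; the other two are that the Ellipse is still implanted and that non-MRI-compatible material has been implanted. The action is "Follow the subject for 30 days post system revision and then withdraw the subject from the study". The required forms are the Baseline, Pre-MRI, MRI, System Revision and Withdrawal CRFs. The Follow Up CRF, which Table 5 assigns to the 1-month visit, is not among them.
- **Table 9, next row.** An Ellipse replaced by another Ellipse, with the same non-MRI-compatible material, is followed to the 1-month visit.
- **Section 6.7, complete explant without replacement.** Sites are to "follow the subject for 30 days, and withdraw the subject from the study". The start of the 30 days is not stated, and the 1-month visit is not mentioned.
- **Table 5.** The 1-month visit is 30 days after the scan, minus 7 or plus 14 days.
- **Section 12.1.1.** A scanned subject enters the safety analysis with a 1-month visit, or with an MRI-scan related complication before it.
- **Sections 8.1.6 and 8.2.** MRI-related complications count up through the 1-month visit, on CEC adjudication. Safety surveillance ends at withdrawal unless the protocol specifies otherwise.

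**The concern.** The two rules run on different clocks. The 6.8.2 text is tied to a visit dated from the scan; the Table 9 row is tied to the date of the revision and ends in withdrawal. A subject who meets all three conditions of that row falls under both.

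In a single-arm safety study, subjects revised soon after the scan are among those a reader most wants to see accounted for. If such a subject is withdrawn before the 1-month visit, with no MRI-related complication on record, 12.1.1 leaves the subject out of the safety denominator. An event first noticed after withdrawal could also be missed, although the endpoint window runs to that visit. For later revisions the mismatch reverses: the 6.8.2 text can end follow-up well before the 30 post-revision days in Table 9 have passed.

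**Working it through.** **1. The plan's own figure.** Inputs from 12.1.1 and 12.2.1: null rate 90%, assumed rate 97%, one-sided 2.5%, exact Clopper-Pearson bound, 90% power. The smallest n from which exact binomial power stays at or above 90% is 141, as stated. At n = 141 the test passes with at most 7 failures (exact alpha 0.0242, power 93.7%).

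**2. Visit window.** 30 − 7 = day 23; 30 + 14 = day 44, counted from the scan.

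**3. When withdrawal precedes the visit.** For a revision on day r, Table 9 withdrawal is on day r + 30, so never before day 30. It precedes a visit on day v only if r + 30 < v.

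| Visit day v | Revision days r with r + 30 < v |
|---|---|
| 23 | none |
| 30 | none |
| 37 | 0 to 6 |
| 44 | 0 to 13 |

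The problem therefore needs a revision within 13 days of the scan and a visit on days 31 to 44. Section 6.7 gives the same result if its 30 days are assumed to start at the explant.

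**4. Later revisions.** For r above 14, r + 30 exceeds 44, so the Table 9 exit falls after the whole window. A day-20 revision gives day 50, against day 23 to 44 under 6.8.2. The difference is 50 − 44 = 6 to 50 − 23 = 27 days of post-revision follow-up.

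**5. Who can drop out of the safety set.** A scanned subject with an MRI-related complication before the visit is included without it and counts as a failure. Only a revised subject with no such complication can be lost, and that subject would otherwise have counted as a success.

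**6. Effect at the margin.** With x failures in n, the lower bound is the 2.5% quantile of Beta(n − x, x + 1).

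| Failures / n | Lower bound | Result against 90% |
|---|---|---|
| 7 / 141 | 90.04% | pass |
| 8 / 141 | 89.13% | fail |
| 7 / 140 | 89.97% | fail |

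At n = 140 only 6 failures are allowed, and power is 87.1%.

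**7. Room for replacement.** Section 12.2.5 freezes the data once 141 subjects have completed the 1-month visit and the arrhythmia condition is met. Up to 165 may be enrolled: 165 − 141 = 24 losses can be absorbed. At the planned 15% attrition, 165 × 0.85 = 140.25, so that room is used up only if attrition reaches about the planned level.

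**The case against.** A reader might infer that the Table 9 rule removes safety failures, or creates missing data selectively among the highest-risk subjects in the device's favour. The documents do not support that. Section 12.1.1 keeps a subject with an MRI-related complication whether or not the 1-month visit takes place, and it does not require adjudication to be finished by then. Losing apparent successes lowers the observed rate, which works against the device. The exception is an event first recognised between withdrawal and a late visit.

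A reader might also infer that everyone who loses the lead is withdrawn early. The row needs all three of its conditions. Nor does 6.7 strictly contradict 6.8.2: section 6.8.1 says "A system revision is defined as a replacement of or repositioning of one or more components of the study ICD system", and 6.7 covers removal without replacement. It is a different case that shares the omission of the 1-month visit.

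Other provisions soften the effect. The visit can always be held within its window before withdrawal. Section 6.15 follows subjects withdrawn for an adverse event until resolution or stability, and 8.2.2 monitors adverse events until resolved. The efficacy sets already exclude leads repositioned or replaced after the scan. Lost subjects would normally be replaced under the enrolment ceiling.

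All of this stands, and it limits the size of the problem. It does not remove the conflict: nothing in the Table 9 row or in 6.7 requires the visit to come first, and the follow-up provisions in 6.15 and 8.2.2 concern events already known.

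**Conclusion.** The conflict between the 6.8.2 text and the Table 9 lead-not-retained row is real and should be reconciled. Its reach is narrow: revision on days 0 to 13 with a visit on days 31 to 44 for early loss, and the opposite mismatch for revisions after day 14. The exposure is lost apparent successes and late-recognised events; recorded failures are not removed.

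The documents give no count of affected subjects. That they will be few is an assumption, based on the three joint conditions. The 7-in-140 example is a boundary case and needs the final safety set to fall one short of 141, which replacement would normally prevent. Section 12.9 leaves withdrawals to a separate SAP that was not supplied, so how these subjects would be analysed cannot be judged here.

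**What to change.** State one study-exit rule for scanned subjects in 6.7, 6.8.2 and Table 9. Before any withdrawal, the subject completes the 1 Month Post Scan safety assessment and its Follow Up CRF. If the lead is gone, this covers adverse events and status without lead measurements. Any 30-day post-revision follow-up is completed as well. Add the Follow Up CRF to the forms in the Table 9 row and in 6.7, and state when the 30 days in 6.7 begin.

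As a separate consistency point, reconcile Table 8 with 6.7 for an enrolled subject whose system is explanted before the scan. Where MRI Settings had been programmed, Table 8 says "The patient will be withdrawn from the study" and gives no follow-up period; 6.7, which applies at any time in the study, gives 30 days. This has no effect on the safety set, because 12.1.1 requires a study scan.

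The cost is a few sentences and at most one already scheduled visit per affected subject.

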6.9 Unscheduled Follow Up

An unscheduled visit is defined as a visit that occurs after the MRI Scan Visit where the subject is seen in clinic due to an ADE, SADE or UADE associated with the Durata or Optisure or Ellipse ICD or for follow up related to the collection of VT/VF episodes. Where possible, perform a device interrogation for the applicable lead(s) to obtain:

- In-clinic bipolar capture threshold at a pulse width of 0.5 ms.
- In-clinic bipolar sensing amplitude. Either the incremental or the automatic (in-clinic, programmer based) method may be used to measure the sensing threshold.
- In-clinic Bipolar lead impedance
- In-clinic HVLI lead impedance

6.9.1 Data Submission

Once testing has been performed, complete and submit the appropriate forms to St. Jude Medical. Refer Table 5: Study Procedures and Data Collection.

It is recommended that the following device printouts and measurements be maintained at the site.

- FastPath Summary
- Test Results with Freezes, Include Battery & Leads
- Wrap-up Overview with full parameters

6.10 Non-Study MRI Scans

A non-study MRI scan is defined as an MRI scan occurring at any time following enrollment up to the conclusion of the subject's participation in the study, excluding the MRI scan performed during the MRI Scan Visit. Non-study MRI scans should be performed per each center's standard of care.

For non-study MRI scans performed at the study center, the same safety data collection and safety precautions outlined at the MRI Scan Visit should be followed. However, if procedures or data are not followed or collected as presented on the non-study MRI Case report form during a non-study MRI scan, it will not be considered a protocol deviation.

MRI Scan Analysis

The MRI scan should be reviewed for obvious abnormalities by a radiologist, and reported to the subject's physician (per standard of care by the facility performing the MRI scan).

Clinical Investigational Plan

The following data should be collected, and reported to St. Jude Medical for non-study MRI scans.

- Date of scan
- Type of scan performed
- Documentation of any Adverse Device Effects
- Device diagnostics, if available
- MRI Scan report, if available
- Fast Path Summary, if available

